9.7.2. Study Populations

The analysis for the Primary Objective will include all enrolled DAA-PASS participants in the prospective cohort. Participants eligible for enrollment are those with their first HCC-free image (see in Section 9.1.1) following HCC treatment intervention(s), HCV RNA positive, DAA-naïve, and BCLC Stage A at the time of initial HCC diagnosis (see Section 9.2.2 and Section 9.2.3). Inclusion of only those who are BCLC Stage A will decrease heterogeneity of the prospective cohort and will provide consistency with the historical cohort.

Subgroups of interest include: (1) participants initiating DAA therapy in the first 6 (≤ 6) months following Enrollment/Baseline, (2) participants initiating DAA therapy > 6 months following Enrollment/Baseline, (3) participants that received DAA therapy at any time following Enrollment/Baseline, (4) participants who achieve SVR following Enrollment/Baseline, and (5) participants who never receive DAA therapy within the follow up period from Enrollment/Baseline.

Information related to the historical cohort and analysis is described in Section 9.7.9.

9.7.3. DAA Exposure as Time-Varying Exposure

Individual participants in the prospective DAA-PASS cohort can contribute person-time to both DAA exposure and no DAA exposure. DAA exposure is a function of time. The no DAA exposure starts at the enrollment/baseline image (Index Date; i.e., successful treatment of HCC) and continues until the participant has an event (i.e., HCC recurrence), initiates DAA therapy, completes the study without initiating DAA therapy, or is otherwise censored. The DAA exposure starts at the first date a DAA is initiated and continues until the participant has an event, completes the study, or is otherwise censored. Participants are censored in whichever exposure type they are in (no DAA exposure or DAA exposure) if they receive IFN treatment, a liver transplant, die, withdraw from the study, or are otherwise removed or lost to follow-up while enrolled in DAA-PASS. Participants that receive DAA therapy starting on the date of Enrollment/Baseline only contribute person-time to DAA exposure and participants that never receive DAA therapy only contribute person-time to the no DAA therapy exposure person-time. The completion of the study is defined by obtaining imaging corresponding to the 24-month follow-up assessment. Note that participants who received a liver transplant while enrolled in DAA-PASS will continue to be followed up to 24 months from Enrollment/Baseline.

Additional information on DAA therapy will be collected including, as available, the DAA prescribed, duration of dosing and planned duration, and SVR response. These will be summarized descriptively.

9.7.4. Coding Convention for HCC Recurrence and DAA as Time-Varying Exposure for the Primary Analysis

This section provides additional details on the coding of the HCC recurrence endpoint for analysis. The primary model of time of onset is based on interval-censoring as outlined in Section 9.7.6.1. The intervals between imaging evaluations are not required to have a fixed length and a participant with a missed visit would simply experience an extended interval -- assuming they have a later follow-up assessment. For the analysis, individuals will have a record of an event or not corresponding to each available interval of no DAA exposure or DAA exposure. The table below provides some examples of participant data where t_{i0} is baseline and t_{ij} for $j = 1$ to n_i represent sequential imaging assessment times for the i^{th} participant:

Table 3. Handling of HCC Recurrence and DAA as Time-Varying Exposure

Situation	Handling in Model
Participant completes study without DAA therapy and without detection of a recurrence event	Participant has n imaging evaluations that define n intervals $(t_{i0}, t_{i1}]$, ..., $(t_{i(n-1)}, t_{in}]$ which are labeled to indicate no events and no exposures have occurred.
Participant receives DAA in an interval and has no events	Participant does not experience recurrence during the study and first receives DAA during $(t_{i(m-1)}, t_{im}]$ with $m \leq n_i$. This and subsequent intervals are labeled as being exposed to DAA initiation. If a participant receives DAA in the first interval, they are included as having DAA therapy from the beginning of follow-up.
Participant has an HCC recurrence detected at time t_{ik} .	Participant experiences a recurrence during $(t_{i(k-1)}, t_{ik})$. For this participant $n_i = k$. Some of the k intervals may be labeled as having no DAA therapy, and some as having DAA exposure.
Participant discontinues prematurely or is censored	Participant has multiple intervals up to the last imaging evaluation at time t_{ik} with $n_i = k$.

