The analyses for the Primary Objective and Secondary Objective B estimate the risk of HCC recurrence associated with exposure to DAA therapy for HCV versus no DAA therapy using a proportional hazards model with DAA therapy included as a time-varying exposure variable. DAA therapy can be initiated at any time after Enrollment/Baseline when absence of detectable HCC is documented (i.e., successful treatment of HCC). For purposes of fitting the statistical model, the time-dependent risk associated with DAA therapy will be assumed to start at the time of the image preceding the start of DAA therapy and is a positive risk in all subsequent intervals. For purposes of these analyses, it will be assumed that the risk of HCC recurrence is a function of DAA exposure only and does not require participants to complete the prescribed HCV regimen or achieve sustained virologic response (SVR). Sensitivity analyses will be used to explore the impact on the estimate of the HR associated with DAA exposure relative to no DAA therapy related to the date of DAA therapy initiation.

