9.7.6.3. Supporting Summaries (Primary Objective)

The following activities are planned to evaluate the robustness of the analysis results to perturbations of the methods and assumptions used, and to fully explore and describe the data.

- Evaluate time to HCC recurrence by treatment of initial HCC.
- Utilize goodness-of-fit measures to explore the appropriateness of the model.
- Evaluate homogeneity of the DAA response across study sites. This may involve only larger sites, pooling, or considering regional differences.
- Descriptive statistics will be used to explore the impact of the period of time the DAA therapy was initiated. A proportional hazards model will also be used to separately code the DAA treatment effect based on those who initiate therapy up to 6 months and after 6 months from the baseline in order to explore the impact of the timing of the initiation of DAA therapy.

- Sensitivity analyses may include: analyses to understand the impact of the proposed handling of DAA therapy that initiates in the interval where a HCC recurrence occurs, an analysis that adds back in the participant follow-up time for those censored due to IFN use, an analysis using time-dependent values of AFP and the MELD score, and an exploration of additional covariates in the model.

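### The protocol gives two start points for DAA exposure, leaves the shared DAA-start and recurrence interval unlabelled in Table 3, and frames its sensitivity analysis by outcome

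*Protocol*

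**What the plan says.** Four places in the protocol bear on how the imaging interval containing the first DAA dose is labelled.

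- **Section 9.3 (DAA exposure).** For model fitting, "the time-dependent risk associated with DAA therapy will be assumed to start at the time of the image preceding the start of DAA therapy", and it stays on in all later intervals. There is no condition on outcome. The same paragraph promises sensitivity analyses on the date of DAA initiation, without naming a coding.
- **Section 9.7.3.** "The DAA exposure starts at the first date a DAA is initiated and continues until the participant has an event". Unexposed time runs until DAA is initiated. Only a participant who starts DAA on the baseline date contributes no unexposed time.
- **Section 9.7.4, Table 3.** The table is introduced with "The table below provides some examples of participant data". The row for a participant with no events opens with "Participant does not experience recurrence during the study and first receives DAA during" a given interval, and its rule for the DAA-start interval is "This and subsequent intervals are labeled as being exposed to DAA initiation"; a start anywhere in the first interval counts as exposed from the beginning of follow-up. The recurrence row says only "Some of the k intervals may be labeled as having no DAA therapy, and some as having DAA exposure".
- **Section 9.7.6.3.** The sensitivity analyses that may be done include "analyses to understand the impact of the proposed handling of DAA therapy that initiates in the interval where a HCC recurrence occurs".

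**The concern.** The primary exposure variable has two definitions. Under Section 9.3 and Table 3, a participant who starts DAA two months after baseline, with the first image at month 3, has no unexposed time. Under Section 9.7.3 the same participant has two months of it. The heading of Section 9.7.4 ties Table 3 to the primary analysis, yet the table omits the case that matters most: DAA start and recurrence in the same interval.

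The sensitivity analysis then selects intervals by their outcome. Its most direct implementation is to relabel or drop the DAA-start intervals that end in recurrence and leave the event-free ones exposed. The exposed group then keeps all its event-free start intervals and loses the ones with events. That is immortal time created by conditioning on the event, and it pushes the hazard ratio towards protection. In a safety study, such a check could be used to explain away a harm signal or to support a finding of no increased risk.

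**Working it through.** **Inputs from the protocol**
- DAA uptake: 42% by 6 months, a further 44% by 12 months, 4% between 12 and 24 months (Section 9.5.1).
- Images at months 3, 6, 9, 12, 18 and 24 (Section 9.2.4, Table 2).
- Recurrence of 15%, 25% or 35% per 12 months. Planned events at N=600: 122 at 15% and 195 at 25%. At N=70 and 35%, 95% bounds of 0.46 to 2.82 (Section 9.5.1).

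**Assumptions added here**
- Constant hazards, no covariates, uptake spread evenly within each period, DAA start independent of recurrence.
- Exponential censoring at a rate fitted to the planned 122 events, because the protocol does not state one.

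**Step 1: reproduce the planned events.** With monthly hazard h = −ln(1 − rate)/12 and censoring rate c, events = N × h/(h+c) × (1 − exp(−24(h+c))).
- At 15%, h = 0.01354. Setting events to 122 gives c = 0.0292 per month.
- At 25%, h = 0.02397. The same c gives 600 × 0.451 × 0.721 = 195, as stated.
- When recurrence counts only if an image detects it before censoring, the simulated numbers are slightly lower: 115 and 184.

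**Step 2: check the precision at N=70, 35%.** The stated bounds imply SE = ln(2.82/0.46)/3.92 = 0.463. The simulation with the start interval exposed for all gives 0.460. The width is reproduced. The endpoints are not (0.41 to 2.46), because the stated interval centres on √(0.46 × 2.82) = 1.14 rather than 1.

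**Step 3: why the direction is fixed.** Let E and n be the events and intervals after the start interval, and E_s and n_s those in start intervals. Labelling all start intervals exposed gives an exposed risk of (E + E_s)/(n + n_s). Relabelling only those with recurrence gives E/(n + n_s − E_s). The E_s events move to the unexposed side without any matching event-free intervals.

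**Step 4: size.** Recurrence times were simulated with the hazard multiplied by the true HR from the actual DAA date. A grouped-time proportional hazards model (complementary log-log with interval effects) was then fitted. Large-sample hazard ratios at 25% and 35% per year:

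| Label of the DAA-start interval | True HR 1 | True HR 2 | True HR 3 |
|---|---|---|---|
| Exposed for all (Section 9.3) | 1.00 | 1.74–1.75 | 2.42–2.45 |
| Unexposed for all | 1.00 | 1.72 | 2.26 |
| Unexposed only if it ends in recurrence | 0.42 | 0.68–0.69 | 0.87–0.89 |
| Dropped only if it ends in recurrence | 0.59–0.60 | 1.06–1.08 | 1.47–1.52 |

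At 15% the first three rows are similar (at true HR 3: 2.46, 2.25 and 0.90). Without censoring, the first row gives 2.48 to 2.54 at true HR 3 and the third gives 0.95 to 0.99.

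**Step 5: mixing the two sections.** Suppose event-free start intervals are exposed throughout, as in Table 3, while recurrence intervals are split at the DAA date, as Section 9.7.3 suggests. The interval contribution is then 1 − exp(−λ(a + HR × b)), with a months before DAA and b months after. The estimates are about 0.60, 1.14–1.16 and 1.68–1.69. The same split applied to every start interval is about unbiased.

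**Step 6: the planned small sample.** At N=70, 35% and true HR 1, about 28.8 recurrences are detected and 15.5% fall in the DAA-start interval: 28.8 × 0.155 ≈ 4.5 events. In 1,500 simulated studies at true HR 1, the recurrence-only relabelling put the upper 95% bound below 1 in 47%, against 3% under the Section 9.3 rule. At true HR 3 it put the upper bound below 3 in 94%, against 8%.

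**The case against.** The strongest reply is that Section 9.3 already fixes the label for everyone, so a start interval that ends in recurrence is exposed. Table 3 offers only examples; its no-event row describes a scenario and does not limit the rule. The wording "intervals may be labeled as having no DAA therapy, and some as having DAA exposure" is what Section 9.3 would produce for someone who starts DAA and later recurs. All of this stands. A reader might infer from Table 3 that the label is fixed only for participants without recurrence. The documents do not support that.

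Nor is the sensitivity work confined to recurrence intervals, since Section 9.3 also commits to analyses on the DAA initiation date in general. Section 9.7.6.3 is optional and names no alternative coding, so the recurrence-only relabelling is one possible implementation and is not prescribed. The SAP, which is not at hand, may settle it.

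One can also read Section 9.7.3 as describing person-time and Section 9.3 as the rule for model fitting. That softens the conflict but does not remove it: Section 9.7.3 carries the heading for the time-varying exposure, does not refer to Section 9.3, and differs from Table 3 on who contributes no unexposed time. The general promise in Section 9.3 does not rule out the biased version either, and the only analysis described for this coding is defined by the outcome.

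**Conclusion.** The point holds as a contradiction and a badly framed sensitivity analysis. Sections 9.3 and 9.7.3 disagree on when exposure starts, Table 3 is silent where DAA start and recurrence share an interval, and Section 9.7.6.3 addresses only those intervals.

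A reader might infer that the plan as written makes a tripling of risk look like no harm in the primary analysis. It does not. Under the Section 9.3 rule a true HR of 1 is estimated at about 1.0, and a true HR of 3 at about 2.4 to 2.5: diluted, but still visible. The values of about 0.42 (true HR 1) and 0.9 (true HR 3) for relabelling, and 0.6 and 1.5 for dropping, belong to a sensitivity analysis that treats recurrence intervals alone. Mixing Table 3 with the Section 9.7.3 date would bias the primary estimate less, to about 0.6 and 1.7.

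All sizes rest on constant hazards, the Section 9.5.1 uptake, censoring fitted to the planned events, no covariates, and DAA start independent of recurrence. The direction of the bias follows from the coding itself.

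**What to change.** 1. Reconcile Sections 9.3 and 9.7.3 to one start rule for model fitting. If Section 9.7.3 is meant only to describe person-time, say so there.
2. In the recurrence row of Table 3, state that the label of the DAA-start interval applies whether or not that interval ends in a recurrence.
3. Reword the item in Section 9.7.6.3 to cover DAA that starts within any imaging interval. Apply each alternative (all exposed, all unexposed, or split at the DAA date) identically to every such interval irrespective of outcome. Exclude any version that relabels or drops only intervals with recurrence.

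The cost is a few sentences in the protocol or SAP. Section 9.2.4.1 already requires DAA therapy details to be recorded and imaging is already collected, so no new data are needed.

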9.7.5. Conventions for Missing Data and Post-Baseline Data Collection

DAA-PASS collects select covariates at the time of screening. Additional data will be collected as it is available within the participant’s record. DAA-PASS has no data collection requirements that are not considered standard of care. Outside of imaging for the assessment of HCC recurrence, data will be available when they appear in the participant’s medical record and are not otherwise considered missing. Details will be provided in the SAP as appropriate.

The analysis of the interval-censored data accommodates missed or unavailable HCC assessments for a given time interval if a later HCC assessment is completed. However, the statistical analyses will include a participant’s data only up to the time of their last completed HCC assessment and will be censored after that time.

9.7.6. Analysis of Early Risk of HCC Recurrence Associated with DAA Therapy (Primary Objectives and Secondary Objective B)

9.7.6.1. Modeling Approach

A Cox proportional hazards model will be used to estimate the relative risk associated with DAA exposure for the time from baseline to HCC recurrence as determined by an absence of detectable HCC on imaging using the HR for the time-dependent DAA exposure variable. The proposed analysis approach is based on a model that uses a time-dependent risk strategy for interval-censored data. The rationale for this approach was based on the following points:

- DAA therapy administration has a natural variation in practice that introduces an accumulation of DAA exposures over time that relates to patient access to medication, considerations of access to transplant that vary with HCV status, and physician practices
- Accommodates the expectation that most HCV positive participants will likely receive DAA therapy at some point in the first 24 months following HCC treatment intervention (i.e., there

will not be a large pool of participants that remain DAA-free to use as a comparison group after this time)

- The use of this approach creates the ability to recruit a larger number of patients under current medical treatment practices from a known cohort where the possible risk associated with DAA therapy is important
- The plan accommodates use of baseline factors that might be associated with outcomes and/or DAA therapy to address potential biases and confounding by indication
- Allows the ability to set a sample size based on desired precision of the risk estimate

Use of the time-dependent risk model for interval-censored data has been utilized successfully for evaluating the impact on risk of an event in many other settings. The time-dependent risk model for interval censored data is discussed in Zeng, Mao, and Ling (2016)¹². Good et al (2015)¹³ demonstrated the use of time-dependent proportional hazards for a colon cancer model of surveillance data. Additional references are Sparling et al. (2006)¹⁴ and Seaman and Bird (2001)¹⁵.

9.7.6.2. Model Parameters

To address the potential for bias in the estimation of the HR of DAA therapy associated with HCC recurrence, baseline factors are included in the risk model based on possible associations of each covariate with time-to-HCC recurrence or possible associations with time-to-DAA therapy. In addition to the time-varying DAA exposure, the model will include the following baseline covariates as available: alpha-fetoprotein (AFP) level, albumin level, platelet count, MELD score, age in years, gender, diabetes status, alcohol use/AUDIT score ≥ 7 , HCC treatment modality, and study centre. In the model, AFP level, albumin level, platelet count, MELD score, and age are interval-scale variables, whereas gender, diabetes status, alcohol use/AUDIT score ≥ 7 , HCC treatment modality, and study centre are categorical variables. Study centre will be included in the model as a random effect.

9.7.6.3. Supporting Summaries (Primary Objective)

The following activities are planned to evaluate the robustness of the analysis results to perturbations of the methods and assumptions used, and to fully explore and describe the data.

- Evaluate time to HCC recurrence by treatment of initial HCC.
- Utilize goodness-of-fit measures to explore the appropriateness of the model.
- Evaluate homogeneity of the DAA response across study sites. This may involve only larger sites, pooling, or considering regional differences.
- Descriptive statistics will be used to explore the impact of the period of time the DAA therapy was initiated. A proportional hazards model will also be used to separately code the DAA treatment effect based on those who initiate therapy up to 6 months and after 6 months from the baseline in order to explore the impact of the timing of the initiation of DAA therapy.

- Sensitivity analyses may include: analyses to understand the impact of the proposed handling of DAA therapy that initiates in the interval where a HCC recurrence occurs, an analysis that adds back in the participant follow-up time for those censored due to IFN use, an analysis using time-dependent values of AFP and the MELD score, and an exploration of additional covariates in the model.

9.7.7. Additional Summaries of Study Data

Descriptive summaries will be provided to assist in the study reporting and may include:

- Information on patient participation, participant study completion status, total duration of follow-up
- Information associated with the participant HCC status including the participant MELD score, Child-Pugh Score, performance status, HCV genotype, and all other factors in the primary model
- Timing of DAA therapy
- Extent of HCC (severity) at initial diagnosis,
- Extent (stage and severity [e.g., number and size of tumors, extrahepatic spread, macrovascular involvement]) and aggressiveness of HCC at time of HCC recurrence, and during follow up after DAA exposure versus no exposure
- Information relating to the overall survival and timing of any deaths

The study may also summarize laboratory values before and after the initiation of DAA therapy or following achievement of SVR (when applicable).

9.7.8. Evaluation of Incidence of HCC Recurrence (Secondary Objectives A and C)

Secondary Objectives A and C are to evaluate the adjusted incidence of recurrence of HCC using the endpoint of the number of events.

An analysis approach based on inverse-probability of censoring weighted averages (IPCW) as outlined in Satten and Datta¹⁶ will be used to obtain an adjusted estimate of the cumulative risk and expected total events for the prospective cohort under the assumption that none of the participants had received DAA. For this analysis, a proportional hazards model of the time-to-censoring event of the non-DAA HCC exposure caused by the start of DAA exposure using the primary analysis covariates will be performed. The model parameters will give individual participants IPC weights in order get an adjusted estimate of the cumulative risk and total events had participants not gotten DAA exposure.

This estimate of risk will be compared to the actual observed risk in the cohort (estimated by the complement of the Kaplan-Meier estimator) to assess the impact of DAA use on HCC recurrence in the prospective cohort. The results will be presented at follow-up time points of 3, 6, 9, 12, 18, and 24 months.

In order to obtain CIs for the estimated risk difference and differences in number of HCC recurrence events at each of the time points, bootstrapping will be used to resample participants from the entire prospective population.

The estimated and actual cumulative event counts will be displayed at the indicated time points. Survival and cumulative event curves will be displayed in figures. Information on significance of the modeling parameters used in the IPCW model will be provided.

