9.9.1. Limitations of Prospective Model and Study Design

The proposed study design was selected based on the expectations of DAA therapy, how HCC recurrence is assessed, and the expected HCC recurrence rate. This study does have limitations because the DAA therapy is not pre-specified and may vary in a manner that affects the precision of estimators. Further, time-dependent covariates may not be completely captured if they are not part of standard of care. Underlying non-ignorable censoring mechanisms, particularly due to potentially high rates of liver transplantation, could potentially bias study results or could reduce precision.

These biases may exist regardless of whether an internal contemporary (i.e., independent from consideration of selection bias) or external historical comparator is used. The use of an internal comparator allows for easier control since data on participants and confounders will be collected in a similar manner between the 2 groups. Factors that differ between patients treated with DAAs and those untreated or not yet treated, may be static (baseline) factors such as demographics and HCC treatment modality or time dependent confounders such as those that occur or change after baseline and which predict DAA treatment and HCC recurrence.

To address the limitations in the study design, especially given that this is a safety study, sensitivity analyses will be used to evaluate the robustness of the primary results to reasonable perturbations of the methods and assumptions used, measures of goodness of fit will be examined, and auxiliary supportive analyses will be used to aid interpretation of the study.

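### One minus Kaplan-Meier with deaths censored overstates the absolute recurrence risks and expected event counts of Secondary Objectives A and C

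*Protocol*

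**What the plan says.** The endpoint for Secondary Objectives A and C is the number of early recurrences (protocol Section 8). Section 9.7.8 sets the method.

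- **No-DAA risk.** An inverse-probability-of-censoring weighted (IPCW) analysis is to give "an adjusted estimate of the cumulative risk and total events had participants not gotten DAA exposure". The cited method paper presents Kaplan-Meier itself as an IPCW average. The weights come from a single model: "a proportional hazards model of the time-to-censoring event of the non-DAA HCC exposure caused by the start of DAA exposure using the primary analysis covariates".
- **Comparison.** "This estimate of risk will be compared to the actual observed risk in the cohort (estimated by the complement of the Kaplan-Meier estimator").
- **Output.** "The results will be presented at follow-up time points of 3, 6, 9, 12, 18, and 24 months". Also: "The estimated and actual cumulative event counts will be displayed at the indicated time points".

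Section 9.7.3 says when follow-up is censored: participants leave the risk set "if they receive IFN treatment, a liver transplant, die, withdraw from the study", or are otherwise lost. Section 9.7.8 does not repeat this rule, and nothing in it suggests another one.

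Section 9.9.1 concedes: "Underlying non-ignorable censoring mechanisms, particularly due to potentially high rates of liver transplantation, could potentially bias study results".

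Section 9.7.9 carries the same approach over to the pooled prospective and historical data for Objective C. Section 9.7.10 promises estimates of cumulative incidence for the historical cohort without naming an estimator.

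**The concern.** A patient who dies without recurrence can no longer contribute one. Kaplan-Meier treats that death like a loss to follow-up: it assumes the patient would have gone on to recur at the same rate as those still under observation. One minus Kaplan-Meier is then the risk that would apply if death were abolished. That can be a legitimate quantity, but it is neither a risk actually observed in a cohort nor a basis for a number of events, which is what Section 9.7.8 says it delivers. The weights do not repair this, because they model only the start of DAA.

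Two outputs are affected. The absolute cumulative risks at all six time points are too high. The expected event counts inherit the same inflation. If the actual counts shown alongside are raw tallies, an inflated no-DAA figure stands next to an uninflated observed one, and DAA could look protective in that table without any true effect. In a safety study that error runs in the reassuring direction.

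**Working it through.** **Step 1: the plan's own counts.** Section 9.5.1 expects 122 and 195 events among 600 participants over 24 months at 15% and 25% annual recurrence, with an unquantified allowance for censoring from transplant or other reasons. Take a constant recurrence hazard L = −ln(1 − r) and a constant censoring hazard m per year:

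events = 600 × L/(L + m) × (1 − exp(−2(L + m)))

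- Without censoring: 600 × (1 − 0.85²) = 166.5 and 600 × (1 − 0.75²) = 262.5.
- With m = 0.35: 122.0 (L = 0.1625) and 195.1 (L = 0.2877). Both planned counts are reproduced.

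So planning assumed substantial censoring. The value of m is inferred, however, and it is not unique: a flat 26% loss gives 123.2 and 194.2. The split between death, transplant and other losses is not stated. I therefore do not use m to size the problem.

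**Step 2: size of the overstatement.** Inputs: 35% recurrence per 12 months (Sections 4.8 and 9.5.1), so L = −ln(0.65) = 0.4308 per year. The annual probability p of the competing event is an assumption, taken as 5%, 10% and 20%, so c = −ln(1 − p) = 0.0513, 0.1054 and 0.2231.

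- One minus Kaplan-Meier at t years: 1 − exp(−L t). This is 35.00% at 12 months and 57.75% at 24 months, whatever c is.
- Cumulative incidence: L/(L + c) × (1 − exp(−(L + c) t)).

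| p per year | 12 months: cumulative incidence | Excess (points) | 24 months: cumulative incidence | Excess (points) |
|---|---|---|---|---|
| 5% | 34.18% | 0.8 | 55.29% | 2.5 |
| 10% | 33.34% | 1.7 | 52.85% | 4.9 |
| 20% | 31.62% | 3.4 | 48.06% | 9.7 |

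Worked line, p = 10%, 24 months: 0.4308/0.5361 × (1 − exp(−1.0723)) = 0.8035 × 0.6578 = 52.85%. The excess is 57.75 − 52.85 = 4.9 points, or 9% in relative terms.

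**Step 3: event counts at 24 months.** Section 4.8 expects 40 to 70 participants.

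- N = 70: 40.4 events by N × (1 − Kaplan-Meier), against 38.7, 37.0 and 33.6 by cumulative incidence. The excess is 1.7, 3.4 and 6.8 events.
- N = 40: 23.1 events, against 22.1, 21.1 and 19.2. The excess is 1.0, 2.0 and 3.9 events.

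**Step 4: the contrast.** If DAA changes neither recurrence nor death, both curves carry the same inflation: 57.75% against 57.75% by one estimator, 52.85% against 52.85% by the other at p = 10%. The difference is zero either way. If DAA left recurrence unchanged but moved the competing probability from 10% to 5%, full exposure against none would differ by 55.29 − 52.85 = 2.4 points of recurrences that really occur, while one minus Kaplan-Meier would show no difference. The two estimators answer different questions, and the plan's wording asks the second while computing the first.

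**The case against.** The best defence is that Section 9.7.8 exists to compare two curves, with bootstrap intervals for the difference. Both are built the same way, so most of the inflation drops out. That stands, under the condition in Step 4. It does not rescue the absolute risks or the expected counts, which are reported in their own right.

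A second defence is size. The protocol states no death or transplant rate, and Section 9.2.2.1 excludes patients with prior or planned transplant for HCC. At 5–10% a year the 12-month excess is only 0.8–1.7 points. That is fair, and it is why the size is given as a range. A third is that the SAP may refine the method. Section 9.7.8 already names the estimator, though, so the SAP would have to depart from it.

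Four stronger readings are tempting and are not supported.

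- *Transplant rules out recurrence, just as death does.* Section 7.2 describes a cohort of 314 transplant recipients in which recurrence was assessed, Section 9.1.1 counts extrahepatic lesions as recurrence, and Section 9.7.3 keeps transplanted participants in follow-up. How transplant is handled is a choice of estimand.
- *All or half of the censoring in Step 1 is death or transplant.* That would put 24-month cumulative incidence at 43.6% or 49.9%, but the rate is back-solved and the shares would be invented.
- *DAA is known to change recurrence-free death.* Two references for Table 1 have titles reporting better survival with DAA. Titles on overall survival, which includes death after recurrence, do not show this.
- *The weights must use time-updated markers.* Section 9.9.1 does name "time dependent confounders such as those that occur or change after baseline and which predict DAA treatment and HCC recurrence", and the weights use baseline values. But neither the direction nor the size of that bias follows from the protocol. Section 9.7.6.3 already lists an optional analysis with time-dependent AFP and MELD for the primary model. Historical data were abstracted at diagnosis and treatment and then at recurrence (Section 9.7.9). With 40–70 participants and 90% assumed DAA uptake, richer weights may be unstable.

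**Conclusion.** The point holds for the absolute quantities. As written, Sections 9.7.8 and 9.7.3 together overstate cumulative recurrence risk and expected event counts whenever recurrence-free deaths occur. Over the assumed 5–20% range and at 35% annual recurrence, the relative excess is 2–11% at 12 months and 4–20% at 24 months. These figures rest on constant hazards, on an assumed competing-event rate, and on reading the censoring rule of Section 9.7.3 into Section 9.7.8. They also take the target to be what actually happens in the cohort, as the protocol's wording implies; a declared net-risk estimand would be a different matter, and none is declared.

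A reader might infer that the primary hazard ratio is wrong too. It is not affected by this point, because censoring a competing event is valid for a cause-specific hazard. Whether transplant censoring is informative is a separate question, which Section 9.9.1 raises but no listed sensitivity analysis takes up. This deserves correction before analysis, but it concerns secondary results only.

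**What to change.** - **Section 9.7.8, and Section 9.7.9 for Objective C:** replace the complement of Kaplan-Meier by the Aalen-Johansen cumulative incidence, IPC-weighted for the no-DAA curve, with death before recurrence as a competing event. Use it for both curves, and derive both event counts from it so that like is compared with like. If raw tallies are also shown, label them as such.
- **Section 9.7.10:** state that cumulative incidence means this same estimator. This is a clarification, since no estimator is named there now.
- **Transplant:** state whether it is treated as censoring or as a competing event in these analyses, and show the other as a sensitivity analysis.
- **Optional:** a sensitivity analysis with time-updated AFP and MELD in the DAA-start weights, in the prospective cohort only and with a sparse model.

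The cost is some wording and a little more programming. Deaths are already recorded (Section 9.2.6), and transplanted participants remain in follow-up (Section 9.7.3). Reported absolute risks will be somewhat lower than under the present text.
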